4.2.3.2 Semiquantitative ^{89}Zr -TLX250 Tumor Targeting

SUVs will be calculated for the tumor bladder lesion, considering the measured tumor-bound activity, the injected activity dose, and the body weight and height of each patient.

4.2.3.3 Quantitative ^{89}Zr activity in blood

The ^{89}Zr activity in the patient blood sample will be determined on day 1 by counting the ^{89}Zr -TLX250 activity in blood in a calibrated gamma counter. Counting will be performed immediately after the end of blood collection in the local nuclear medicine department in order to check the absence of activity from residual ^{89}Zr -TLX250 in blood.

4.2.3.4 Independent Central Histological analysis

An independent central histology analysis will be carried out at ICO Saint Herblain. The purpose of this analysis is the determination of the degree of CAIX expression from TURBT or cystectomy tumor sample by immunohistochemistry.

The degree of CAIX expression will be investigated and classified.

4.3 Treatment Assignment

Once full establishment of eligibility by the site, the physician will confirm patient eligibility, the patient number will be allocated and ^{89}Zr -TLX250 imaging should be scheduled before the administration of the study drug.

Then, the authorized site representative for the study can order the study drug through the “⁸⁹Zr-TLX250 Order Form”.

4.4 Blinding

Not applicable, this is an open-label study.

4.5 Treatment Compliance

⁸⁹Zr-TLX250 will be administered by trained study personnel at the site. Details of each administration will be recorded in the patient file and in the eCRF.

4.6 Radiation Precautions

Medical administration of radioactive diagnostic tracers such as ⁸⁹Zr-TLX250 is guided by national radiation safety regulations, differing extensively between countries.

Excretion limits acceptable for discharge will be defined by the investigators in compliance with the local regulations. Commonly, patients will be discharged from the hospital 3 hours p.a., unless the investigator decides otherwise.

Excretion will occur during the rinsing stage after instillation. No excess excretion is expected after rinsing. If happens, only a low fractionation of leakage could occur days after. This is what will be studied with quantified imaging of the bladder. The leakage, if any, will be at very low level, lower than excretion of standard diagnosis examination after patient release.

Patients will be encouraged to increase fluid intake and to void frequently through the first day after administration.

The following safety precautions apply for patients for one week:

- Patients should be advised to observe rigorous hygiene in order to avoid risk of contamination of others using the same toilet facility.
- One shower per day.
- Change of underwear every day.
- A double toilet flush is recommended.
- Patients should wash their hands thoroughly every time after using the toilet.

After hospital discharge, **no distancing from and contact to other persons is required**.

The following precautions apply for health care workers:

Healthcare personnel are advised to adhere to their SOPs and/or any guidance and regulations for handling radioactive substances. It is mandatory to use protective high quality (latex/nitrile) gloves in any direct contact with the radiopharmaceutical (vial/syringe).

A simple calculation with RAD PRO CALCULATOR software, shows that at 100cm from a 37MBq ^{89}Zr point source, the dose rate is 4.5 $\mu\text{Sv}/\text{h}$. Considering 10 cm of water as shielding due to the body, it reduces the dose rate to 3.8 $\mu\text{Sv}/\text{h}$. In reality, a fraction of the activity will be remained into the bladder so we could expect one tenth or even one hundredth of the activity and so the dose rate at 100cm. As comparison, the releasing rule for a patient after iodine-131 treatment impose a maximum dose rate of 20 $\mu\text{Sv}/\text{h}$ at 100cm.

4.7 Total Radiation Exposure

^{89}Zr -Girentuximab will be administered by intravesical instillation, and should remain inside the bladder. The Low Dose CT scan will be performed using a hybrid camera. No dose to organs at risk is expected.

If in the worst case, there is a release of the product into the rest of the body, the dosimetry data shows a very low impact as it is not of the order of 37MBq (as for intravenous administration) but rather of 1 MBq (for intravesical instillation).

Radiation dosimetry was evaluated in a bridging dosimetry study (ZIRDOSE study) investigating the safety and tolerability of ^{89}Zr -Girentuximab. The whole body effective dose for intravenous administration of ^{89}Zr -Girentuximab in this phase 1 study was $0.487 \pm 0.014 \text{ mSv}/\text{MBq}$ using the most widely established dose calculation tool OLINDA 1.1 and the ICRP 60 standard (23). The absorbed/effective dose was calculated accordingly and resulted in a total whole body effective dose of $18.0 \pm 0.5 \text{ mSv}$ for 37 MBq. When a newer software IDAC-Dose 2.1 and the ICRP 103 standard (24) is used, the resulting effective dose will be $0.551 \pm 0.030 \text{ mSv}/\text{MBq}$ or $20.5 \pm 1.1 \text{ mSv}$ for 37 MBq.

4.8 Prior and Concomitant therapy

At baseline screening, all prior cancer-related treatments are to be recorded.

All bladder medications taken within 30 days before ^{89}Zr - Girentuximab PET/CT exam should be recorded on the case report form.

4.8.1 Permitted concomitant therapy

TransUrethral Resection of Bladder Tumor (TURBT) in the 30 days after ^{89}Zr - Girentuximab is permitted only if the patient's condition requires it.

4.8.2 Prohibited concomitant therapy

Chemotherapy, radiotherapy (other than short cycle of palliative radiotherapy), immunotherapy are prohibited within 21 days of ^{89}Zr -girentuximab administration.

These treatments are prohibited within 30 days of ^{89}Zr -girentuximab administration:

- Experimental diagnostic or therapeutic drugs.
- Any radiopharmaceutical exposure.

[figure not shown]
5. STUDY DESIGN

5.1 Overview of study design

The research presents the following characteristics:

- Feasibility pilot study
- Imaging trial
- Monocentric
- Non randomized
- Uncontrolled
- Open-label
- Prospective

5.2 Study design schedule

* If ^{89}Zr -Girentuximab D1 Blood dosing is positive, a Whole body imaging should be done, if negative, a bladder imaging should be performed

Figure 1: Study design schedule

6. STUDY PROCEDURES: DESCRIPTION AND SCHEDULE

Before study entry, throughout the study, and following study drug discontinuation, various clinical and diagnostic laboratory evaluations are outlined. The purpose of obtaining these detailed measurements is to ensure adequate safety and tolerability assessments. Clinical evaluations and laboratory studies may be repeated more frequently if clinically indicated. The Schedules of Assessments during the screening and treatment period is provided following the Protocol.

6.1 Screening visit

Screening procedures will be performed up to 30 days before ⁸⁹Zr- Girentuximab administration. All patients must first read, understand, and sign the ICF.

No trial-related procedures will be initiated before the signed consent has been obtained.

After signing the ICF, completing all screening procedures, and all eligibility criteria confirmed, patient will be enrolled in the study.

All procedures performed prior to the signing of the ICF and considered as standard of care may be used as screening assessments if they are performed within the 30 days prior to ⁸⁹Zr-TLX250 administration.

The following procedures will be performed during the Screening period:

- Informed Consent
- Subject registration and subject number assignment
- Review of eligibility criteria and confirm eligibility
- Demographics
- Record Medical History
- Record Disease History: Histopathological TURBT report
- Record NMIB - related treatments
- Perform full physical examination with ECOG Performance Status and Vital signs
- Review of prior/concomitant bladder medications
- Imaging exams: cystoscopy report + bladder diagram
- Standard laboratory samples for Haematology and serum Chemistry.
- Urine cytobacteriological testing: to be performed, before ⁸⁹Zr-Girentuximab order: within 10 days before ⁸⁹Zr-Girentuximab administration.
- Serum β-HCG pregnancy test in women of childbearing potential* and Urine Pregnancy test within 72 hours before ⁸⁹Zr-TLX250 administration. Pregnancy test should not be performed for postmenopausal patients**.

* The women under 55 (<55) are considered with childbearing potential.

** A postmenopausal state is defined as no menses for 12 months without an alternative medical cause.

6.1.1 Medical history

NMIB Disease history will be reported, including date of diagnosis, histological results and previous NMIB cancer treatments.

Relevant findings from medical history (obtained at screening) and physical examination will be reported.

Relevant bladder concomitant medications will be reported.

6.1.2 Physical examination and vital signs

A complete physical examination will be performed within 30 days before patient enrolment.

The performance status will be assessed.

Vital signs (blood pressure [BP], pulse, and temperature), Body weight and height will be evaluated.

6.1.3 Urine cytobacteriological testing

A urine cytobacteriological testing will be performed before ⁸⁹Zr-Girentuximab order: within 10 days before ⁸⁹Zr-Girentuximab administration. This testing should be negative before intravesical instillation to ensure the absence of germs before instillation.

6.1.4 Laboratory evaluations

The following laboratory tests will be performed:

- ⇒ Haematology: Haemoglobin, haematocrit, platelets, red blood cells, White blood cells and differential (neutrophils, basophils, eosinophils, lymphocytes, monocytes).
- ⇒ Chemistry: Creatinine, urea, SGOT (AST), SGPT (ALT).
- ⇒ Blood or urinary Pregnancy test

6.2 Enrolment

Patient Enrolment may occur only after the completion of the screening evaluations and confirmation of subject eligibility.

Enrolment will be centralized and performed via the eCRF.

How to connect to the eCRF:

- Go to website: <https://www.cancero-go-online.org/CSOnline/>
- Study code: **CRGA0067**
- Study Sponsor number : ICO-2021-03
- Username and password: Nominative and personal, they will be given to each participant after investigation site participation setup visit opening of the site.

If the software is unavailable, the enrolment registration request will be centralized at the sponsor ICO “Service Promotion de la Recherche Clinique”. A registration Form is provided for this purpose.

It will be sent by e-mail to the sponsor (between 9am and 5pm). An enrolment number will be assigned to the patient and e-mailed to the site.

Sponsor Contact Information : DRC de l'ICO / Cellule de Promotion

[contact]

Project Manager: [name]

E-mail: [contact]

After the enrolment procedure is completed, the investigator will receive by email a confirmation of the patient enrolment, the centre identification number, the patient identification number.

After the enrolment, each patient will receive a “**patient card**” (Appendix 6) specifying the procedure received in the trial. The patient may present this card to any health professional encountered during the trial.

6.3 ^{89}Zr -TLX250 PET/CT Imaging

6.3.1 ^{89}Zr -TLX250 administration

The following examinations and procedures will be performed on Day 0 before ^{89}Zr -TLX250 administration:

- Patient performance status.
- Pre-dose Vital signs.
- Blood or urine Pregnancy test (for female patients of childbearing potential) within 72 hours before ^{89}Zr -TLX250 administration.
- Baseline findings.
- Bladder concomitant medications.
- Urine dipstick analysis before ^{89}Zr - Girentuximab administration.

The ^{89}Zr -girentuximab solution will be administered through an intravesical instillation using natural urinary tract (see section (5.2.1)).

Vital signs will be assessed before; 2; 4; 20 and 44 hours after ^{89}Zr -TLX250 administration.

Adverse event monitoring will be assessed within 2 hours post administration and reported in the medical file and the e-CRF.

6.3.2 ^{89}Zr -TLX250 PET/CT Imaging and Dosimetry

Several PET/CT images acquisitions should be performed at the end of ^{89}Zr -girentuximab administration on D0, D1 and D2 (see section 4.2.2).

Urine dipstick analysis at D1 and D2 of ^{89}Zr - Girentuximab administration

A blood sample (one heparin tube of 4 ml) will be drawn on day 1 to evaluate quantitative biodistribution of ^{89}Zr -TLX250 in blood (see section 4.2.3.3).

6.4 Follow-up visit: Day 30 following ^{89}Zr -TLX250 administration

End of study visit will be performed 30 days after ^{89}Zr -TLX250 administration.

All procedures bellow should be performed:

- Evaluation of Performance Status (WHO)
- Urine cytobacteriological testing

- Review of AE and SAE + concomitant medications

6.5 Study discontinuation

The study could be interrupted or terminated by the sponsor in agreement with the coordinator and with the competent authorities for the following reason:

- Occurrence of significant previously unknown adverse reactions or unexpectedly high intensity or incidence of known adverse reactions described such as: any adverse grade > 3 in 2 patients/3.
- recruitment of patients too low,
- poor quality of the data collected,

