Overall, no toxicity at all was observed in both preclinical and clinical studies.

The antibody used in the PERTINENCE study is different but the same retention inside the bladder should be expected due to the size of the antibody molecule.

The radionuclide also is different but a higher toxicity could be expected with alpha-emitting bismuth-213 radionuclide than with positron-emitting zirconium-89 due to a much higher Linear Energy Transfer (LET).

Consequently, no toxicity at all is expected in the PERTINENCE study after intravesical instillation of 37 MBq of ^{89}Zr -girentuximab.

According to the information described above, it appears that the benefit/risk ratio will be clearly in favour of the benefit to the patient.

The results of Pertinence study may contribute to the development of a new targeted therapy for Non-Muscle-Invasive Bladder Cancer (NMIBC) with girentuximab labelled with a therapeutic radionuclide such as astatine-211 (^{211}At -Girentuximab).

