7.1 Definitions

7.1.1 Adverse event Definition

An adverse event (AE) is defined as any untoward medical occurrence, in a patient or clinical trial subject treated by a medicinal product and which **does not necessarily have a causal relationship with this treatment**.

Intensity (severity):

Intensity of adverse events is assessed by the investigator. The intensity criterion should not be confused with the seriousness criterion, which is the guide for defining the reporting requirements.

The intensity of adverse events will be classified according to the NCI-CTCAE Version 5.0.

For any event not listed in this classification, the classification will be assessed as follows:

- **Mild** (grade 1): does not affect the patient's Activities of Daily Living (ADL)
- **Moderate** (grade 2): disrupts the patient's ADL
- **Severe** (grade 3): disabling; limiting self-care ADL
- **Life-threatening** (grade 4): urgent intervention indicated.
- **Death** (Grade 5)

Causal relationship to study drug/procedure:

Relationship between the AE and the study drug /procedure must be assessed following EVCTM (EudraVigilance Clinical Trial Module) criteria: reasonable possibility / no reasonable possibility. Important factors to be considered in assessing the relationship of the AE to study treatment include:

- The temporal sequence from drug/procedure administration
- Recovery on drug discontinuation (de-challenge), recurrence on drug re-introduction (re-challenge).
- Underlying, concomitant, intercurrent diseases.

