7.1.5 New Safety Issue

Any new data that may lead to a reassessment of the benefit/risk ratio of the trial, or that may be sufficiently important to consider changes in the conduct of the study, or trial-related documents, or that may lead to the suspension, termination or modification of the study protocol or similar trial.

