7.2.2.3 Notification to the sponsor

The investigator must **immediately (without delay)** and **no later than 24 hours** following knowledge of the event, notify the sponsor pharmacovigilance unit of **any SAE or any new issue** defined in sections 7.1.2 and 7.1.5:

- **From informed consent signature up to ⁸⁹Zr-girentuximab administration:** only SAE related to the study procedures must be reported to the sponsor.
- **From ⁸⁹Zr- girentuximab administration up to 30 days post-⁸⁹Zr- girentuximab administration:** all SAEs, whether or not related to the study drug/procedure, must be reported to the sponsor.

All delayed Serious Adverse Events (occurring after this period) considered reasonably related to ⁸⁹Zr- girentuximab must be reported without time limit.

Except those that are identified in the protocol as not requiring immediate reporting.

This initial SAE notification shall be followed promptly by a detailed written follow-up report(s) until event resolution.

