7.3.4 Notification of New Safety Issue

The sponsor is responsible for alerting the principal investigator in case of identification of a New Safety Issue and should propose urgent measures to be implemented.

The sponsor is responsible for reporting to the competent authorities, **without delay**, any New Safety Issue and the proposed measures.

Relevant follow-up information regarding any New Safety Issue should be reported to the competent authorities within a new delay of 8 days.

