11. COLLECTION AND MANAGEMENT OF RESEARCH DATA

11.1 Collection of study data

11.1.1 Collection and conservation of study data

The data will be collected via an electronic Case Report Form (eCRF) accessible from a secure internet connection, allowing traceability of data access and modifications.

A Case Report Form (eCRF) will be created per patient. All the information required by the protocol must be provided in the CRF within 15 days following its availability. The CRF will include the data needed for statistical analyses based on the study objectives, as well as the data needed to detect major deviations from the protocol (inclusion and non-inclusion criteria, premature discontinuation and causes, follow-up of protocol visits and examinations, collection of adverse events and concomitant treatments).

Data entry will be performed online by Investigators and authorised staff identified in the Delegation of Responsibilities Form for each site. This form is kept in the investigator Master file.

The study data are under the responsibility of the Director of "Institut de Cancérologie de l'Ouest".

Until the results are published, the study data will be hosted on a centralised server provided by the company ENNOV. An ISO 9001:2008 approved bi-site data hosting centre ensures data storage, protection and security (Data Centre in Poitiers and Roubaix, mirror sites). Exports are carried out in parallel in a secure area of the ICO's information system servers for carrying out analyses.

The study data and essential documents will then be archived **for a minimum period of 15 years**, either on the ICO's premises or with a service provider specialising in medical archiving.

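### Section 6.5 does not hold the next dose after a first severe related reaction, and its only numeric example (grade 4-5 in two of three unspecified patients) is too lax for this six-patient tracer study

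*Combined protocol and SAP*

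**What the plan says.** Section 6.5 states that the study "could be interrupted or terminated by the sponsor in agreement with the coordinator and with the competent authorities" for listed reasons. The safety reason has two limbs: significant reactions not known before, and known reactions that are unexpectedly intense or frequent. The second limb ends with an example, "any adverse grade > 3 in 2 patients/3". Grading follows CTCAE version 5.0 (section 7.1.1), so grade above 3 means life-threatening or fatal.

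Reporting runs on a separate track. Section 7.1.1 says: "The intensity criterion should not be confused with the seriousness criterion, which is the guide for defining the reporting requirements". Section 7.2.2.3 requires notice to the sponsor within 24 hours of "any SAE or any new issue". Section 7.1.5 defines a New Safety Issue to include data "that may lead to the suspension, termination or modification of the study protocol or similar trial", and under section 7.3.4 the sponsor "should propose urgent measures to be implemented". For everything else, section 11.1.1 applies: "All the information required by the protocol must be provided in the CRF within 15 days following its availability".

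Section 1.4.1 states that patients gain nothing individually. Section 1.4.4 concludes that "no toxicity at all is expected in the PERTINENCE study after intravesical instillation of 37 MBq". Section 8.1 describes a first-in-man intravesical procedure in six patients, needed to confirm sufficient safety for later patients. Sections 9.1.1 and 9.1.2 provide for neither a data monitoring committee nor a steering committee.

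**The concern.** Where no toxicity is expected and the patient gains nothing, one severe related reaction already contradicts the premise on which the next patient would be dosed. The plan's only number for unexpectedly high intensity or incidence is nevertheless set at two grade 4-5 events among three patients. The example does not say which three, and it omits the noun after adverse. The stem speaks of reactions, so related events are probably meant.

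The larger gap is that no section in the available text says the next instillation waits while a first severe reaction is reviewed. The plan gives powers and reporting duties but no default. There is no stated minimum interval between patients and no committee that would impose a hold. The next patient could therefore be dosed before anyone has decided whether that is acceptable.

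**Working it through.** The documents state no operating characteristic for section 6.5, so there is no figure to reproduce. The checks below use six patients (section 8.1), a 12-month enrolment period (Trial Calendar) and the 15-day eCRF deadline (section 11.1.1). All event rates are assumptions, because the documents give none for this route. Patients are treated as independent.

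**1. How much the missing denominator matters, with no assumed rate.** If exactly two of six patients have a grade 4-5 event, there are C(6,2) = 15 patterns. The example is met in:
- two of the first three: C(3,2) = 3
- two of any three consecutive: 5 adjacent pairs + 4 pairs one apart = 9
- two in either block of three: 3 + 3 = 6
- two thirds of all six (four of six): 0

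**2. Chance that the example is met, for an assumed grade 4-5 rate p.** Two of the first three: 3p²(1−p) + p³. At p = 0.20 this is 0.096 + 0.008 = 0.104. Two blocks: 1 − (1 − 0.104)² = 0.197. The consecutive reading is enumerated over the 2⁶ outcomes. Four of six is the binomial tail, 0.017 at p = 0.20.

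| p | first three | any three consecutive | either block | four of six |
|---|---|---|---|---|
| 0.05 | 0.7% | 2.1% | 1.4% | 0.01% |
| 0.20 | 10.4% | 24.6% | 19.7% | 1.7% |
| 0.50 | 50.0% | 79.7% | 75.0% | 34.4% |

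**3. How often a first-event pause would be reached.** Here p is an assumed rate of related grade 3 or higher reactions: 1 − (1−p)⁶ = 5.9% at p = 0.01, 26.5% at 0.05 and 73.8% at 0.20. These are different events from those in step 2, so the two sets should not be compared at a common rate.

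**4. Chance that an affected patient is followed by another dose within 15 days.** Assume six independent dosing dates, uniform over 365 days. The chance that j given gaps all reach 15 days is (1 − 15j/365)⁶. With k the number of the five gaps shorter than 15 days, the chance sought is

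1 − E[(1−p)^k] = 1 − Σ_j C(5,j) p^j (1−p)^(5−j) (1 − 15j/365)⁶, for j = 0 to 5.

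This gives 1.1% at p = 0.01, 5.5% at 0.05 and 20.6% at 0.20. The 15 days are counted from the affected patient's dose, and the timing of the reaction is not modelled. If dosing were evenly spaced, about two months apart, the result would be zero.

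**The case against.** Several stronger readings are tempting, and the documents do not support them.

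- *A reader might infer that the sponsor cannot act until two grade 4-5 events occur.* It can. The clause is discretionary and the figure is an example attached mainly to known reactions. The previously-unknown limb carries no count. SAE notice and the New Safety Issue steps can each lead to suspension after one event.
- *A reader might infer that grade 3 reactions generally wait for eCRF entry.* Section 7.1.1 describes grade 3, for events not listed in CTCAE, as disabling. Section 7.1.2 counts significant disability as serious, defines it to include a temporary clinically significant handicap, and adds important medical events. Many grade 3 reactions are therefore already under the 24-hour duty. Because the plan expects no tracer-related event, one would also be hard to keep outside section 7.1.5. The remaining reporting gap is grade 3 reactions that are neither serious nor judged a New Safety Issue. These are mainly the known instillation effects in section 7.1.3, such as fever or haematuria.
- *A reader might take the chance that some two patients are dosed close together as the risk.* It is not, because an event must come first. Step 4 gives the joint chance, and requiring that the reaction also went unnotified would lower it further.

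The setting also helps. There is one site, the sponsor's own radiopharmacy prepares the doses (section 4.2.1), and each dose is ordered individually (section 4.1.5.1). The people who see a reaction can withhold the next order. A hold might also be written in Appendix 1 or Appendix 7, which were not available.

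All of this stands and narrows the point. It shows that the sponsor is able to pause and probably would, but it does not supply a written default.

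**Conclusion.** The point holds in a limited form. The numeric example in section 6.5 is too lax for this study and has no clear denominator. No available section holds the next dose while a first severe related reaction is reviewed. What is missing is a default, since the authority to stop is already there.

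The size is modest and rests on assumed rates: about 1%, 5.5% or 21% of trials with an affected patient followed by another dose within 15 days, at related grade 3+ rates of 1%, 5% or 20%, given independent patients and uniform dosing dates. The plan's own expectation of no toxicity points to the low end. The finding that the example is met in 3, 9, 6 or 0 of 15 patterns needs no assumed rate. This is a cheap improvement worth considering. It does not show that the trial is unsafe as run. Confidence is medium, mainly because two appendices could not be read.

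**What to change.** Add to section 6.5, in place of the example:

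> Dosing of further patients is paused after the first grade 3 or higher adverse reaction with a reasonable possibility of relation to ⁸⁹Zr-girentuximab or the instillation (assessed as in section 7.1.1), until the sponsor and coordinator have documented whether to resume, amend or stop. The investigator informs the sponsor of such a reaction within 24 hours, serious or not. Events after TURBT or cystectomy with no reasonable possibility of relation do not count.

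Keep the existing stem, including agreement with the competent authorities, as the grounds for termination. If the two-of-three example is also kept for termination, state which patients it counts and that it means related reactions.

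**Cost.** A few sentences and a protocol amendment, with ethics committee and ANSM authorisation where applicable (section 10.3). No extra patients, visits or procedures. An unneeded review would occur in about 6% of trials at a true rate of 1% and 26% at 5%, sometimes for a single grade 3 instillation effect. A pause may lose a candidate, because cancer treatment is not delayed for the study (section 3.1). An included patient who is not dosed is replaced (section 3.5), and a dose can be cancelled at any time (section 4.1.5.1).

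**Limit.** The pause sets no minimum interval, so a late reaction within the 30-day window (section 7.2.1) could still follow the next dose. The documents give no basis for choosing such an interval.
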